NOTE: Email [contact] to set up the N:\Research-Studies network Drive, if needed. For any questions regarding REDCap, please contact the UNM Health Sciences Clinical and Translational Center (CTSC).

All surveys, and study materials will be coded with a unique study ID number assigned at enrollment. The link to study ID numbers will be stored on the secure REDCap server at the UNM HSC CTSC and only authorized, IRB approved study team members will have access to the information. The link will be destroyed when the study is complete. Only de-identified data labeled with the unique study ID will be exported from REDCap and used in analyses. All data files used during the data analysis will be stored on the N:\Research-Studies network drive. Only de-identified data in aggregate will be exported from REDCap and used in analyses.

All data collected via mEMA are de-identified. The mEMA platform does not require collection of any personal identifying information. The system automatically generates a unique identifying code that is assigned to participants to enter into the mEMA App. The key linking this code to the unique participant study ID is stored outside of the Ilumivu mEMA system in the secure HSC REDCap database and only authorized study personnel will have access. Data are sent from the wearable Garmin sensor to the mEMA app on the participant's smart phone and then uploaded to Ilumivu's servers when the participant is within WiFi range. All data are encrypted before being pushed to the Ilumivu cloud-based storage database. Access to the database is restricted to authorized research personnel. Only research personnel authorized by the PI can directly access the secure cloud-based storage database to download data in CSV file format. All data files will be stored on the N:\Research-Studies network drive

Research records will be maintained for at least 6 years after study completion and then destroyed per the following policy: HSC-R-801 PR.1 "Research Data and Materials Retention Policy" and then destroyed. After study closure, long-term data storage must be in the N:\Research- Studies network drive.

16.10. Describe any procedures that will be used for quality control of collected data and/or specimens.

- What information will be included in the data or associated with the specimens?*

- *How will data be collected and what is the data type (i.e. electronic, hard copy, specimen, etc.)?*

Data will be collected via survey using the secure REDCap server at the UNM HSC CTSC and only authorized.

All data collected via mEMA are de-identified. The mEMA platform does not require collection of any personal identifying information. The system automatically generates a unique identifying code that is assigned to participants to enter into the mEMA App. Data are sent from the wearable Garmin sensor to the mEMA app on the participant's smart phone and then uploaded to Ilumivu's servers when the participant is within WiFi range. All data are encrypted before being pushed to the Ilumivu cloud-based storage database. Access to the database is restricted to authorized research personnel. Only research personnel authorized by the PI can directly access the secure cloud-based storage database to download data in CSV file format. All data files will be stored on the N:\Research-Studies network drive.

The PI has completed the HSC-ISO Cloud Bases Security System Review (see attachment H) as well as the required User Policy (see Attachment I)

- *How long will the data or specimens be stored? See sections 16.15 – 16.17 for data storage requirements.*

Research records will be maintained for at least 6 years after study completion and then destroyed per the following policy: HSC-R-801 PR.1 "Research Data and Materials Retention Policy" and then destroyed. After study closure, long-term data storage must be in the N:\Research- Studies network drive.

- *Who will have access to each method of data collection and/or specimens?*

Only authorized, IRB approved study team members will have access to the information.

16.11. How will the data and specimens be transported. Describe if data will be collected, transmitted, and/or stored via the internet, the identifiability of the data, and the security measures that will be employed to protect it (if data is de-identified, explicitly state that).

All data collected via mEMA are de-identified. The mEMA platform does not require collection of any personal identifying information. The system automatically generates a unique identifying code that is assigned to participants to enter into the mEMA App. Data are sent from the wearable Garmin sensor to the mEMA app on the participant's smart phone and then uploaded to Ilumivu's servers when the participant is within WiFi range. All data are encrypted before being pushed to the Ilumivu cloud-based storage database. Access to the database is restricted to authorized research personnel. Only research personnel authorized

by the PI can directly access the secure cloud-based storage database to download data in CSV file format. All data files will be stored on the N:\Research-Studies network drive.

The PI has completed the HSC-ISO Cloud Bases Security System Review (see attachment H) as well as the required User Policy (see Attachment I)

16.12. Describe if data will be collected by audio or video recording, how the recordings will be secured, whether and when recordings will be transcribed, if the transcription will include identifiers, if, when, and how the recordings will be deleted. Describe if the subjects will have the opportunity to review the recordings and request full or partial deletion. If the recordings may include persons other than the subjects, describe how this will be managed.

N/A

16.13. Describe if the data will include photographs, what will be included in the photographs, and how the photographs will be secured. Describe if subjects will have the opportunity to review the photographs and request destruction. If the photographs may include persons other than the subjects, describe how this will be managed.

N/A

16.14. The National Institutes of Health (NIH) has issued the Data Management and Sharing (DMS) policy effective January 25, 2023, to promote the sharing of scientific data. The NIH Policy for Data Management and Sharing (NOT-OD-21-013) requires researchers to include a data management and sharing (DMS) plan in funding applications. The DMS Policy applies to all research, funded in whole or in part by NIH, that results in the generation of scientific data. If applicable, complete HRP – 234 – FORM – NIH Data Management and Sharing Policy and upload to the study record at time of initial new study submission. At time of study closure, complete HRP-235 – FORM – NIH Data Management & Sharing Policy_Study Closure Form. Clarify if this policy applies.

N/A

16.15. State how long research record will be maintained. Note: Federal regulations require that research records will be maintained for at least 3 years after study completion and then will be destroyed.

Research records will be maintained for at least 6 years after study completion and then destroyed per the following policy: HSC-R-801 PR.1 “Research Data and Materials Retention Policy” and then destroyed. After study closure, long-term data storage must be in the N:\Research- Studies network drive.

16.16. Research records of minors (under 18) must be retained until the minor turns 22 years old per the following policy: HSC-R-801 PR.1 “Research Data and Materials Retention Policy” and then will be destroyed.

N/A

16.17. *HIPAA Requirements: Any research that involved collecting identifiable health information is subject to HIPAA requirements. As a result, records must be retained for a minimum of 6 years after each subject signed an authorization, and then will be destroyed.*

17. Data and Specimen Banking

17.1. *If data or specimens will be banked or archived locally for future use, provide the name and study number of the repository that they will be deposited into. Describe exactly what data or specimens will be banked and for what purposes, and whether the data or specimens will include identifiers, be coded, or be fully stripped of all identifiers with no code or key that would allow relinking. Be certain to describe the banking in the primary consent. A separate consent and authorization, if applicable, will be necessary for the banking activity itself and is typically provided by the repository. If you need to establish a repository for the purposes of banking or archiving data or specimens, a separate submission for the repository is needed as this is considered to be a distinct research activity under the regulations.*

N/A: we will not be banking data or specimens. All data will be stored in the HSC-maintained and secured REDCap data base or on the N:\Research-Studies network Drive.

17.2. *If this is a multi-center study, and/or if data or specimens will be banked or archived elsewhere, identify who the holder of the data or specimens will be, exactly what data or specimens will be banked and for what purposes, and whether the data or specimens will include identifiers, be coded, or be fully stripped of identifiers with no code or key that would allow relinking. A Materials Transfer or other agreement may be necessary, please consult with the HSC Sponsored Projects Office at [contact] or by email at [contact]. Material Transfer Agreement procedures may be found at <http://hsc.unm.edu/financialservices/preaward/ancillary-agreements/material-transfer-agreements/procedures.html>. Be certain to describe the banking in the consent and authorization, using opt-in procedures, and the procedures for subjects to request withdrawal of their data or specimens and any limitations on their ability to do so.*

18. Risks to Subjects

18.1. *List the reasonably foreseeable risks, discomforts, hazards, or inconveniences to the subjects related to the subjects' participation in the research. Describe the probability, magnitude, duration, and reversibility of the risks. Consider physical, psychological, social, legal, and economic risks. Note that almost all research includes the risk of a breach of confidentiality and/or privacy.*

18.2. *If applicable, indicate which procedures may have risks to the subjects that are currently unforeseeable.*

There are minimal risks to participants from this research. Since breach of confidentiality is the most likely risk, participants will be administered informed consent privately in order to insure anonymity. All data collected as part of the study will be identified with a study number. Any forms and survey results that are obtained will be securely stored in either an encrypted database or on the N:\Research-Studies network Drive. Any links between personal identifying information and study ID will be destroyed upon completion of the study.

Each participant will complete surveys regarding mental well-being (e.g. anxiety, stress). These surveys may cause discomfort or stress. To minimize stress, all interviews will be conducted in a private room in a non-judgmental manner by trained research personnel. We will encourage all study participants to discuss concerns about mental health or other health issues with their health-care provider. Additionally, meditation is generally not considered harmful, however, it is possible a participant may experience some discomfort while participating in meditation. Meditation can reveal uncomfortable thoughts or emotions. If a participant experiences distress, a trained research team member will provide the participant with information related to the UNM Counseling, Assistance, & Referral Services (CARS).

Yoga is generally considered to be a safe form of physical activity when performed properly under the guidance of trained instructors. However, as with other forms of physical activity, there is always a chance that an injury may occur. Most common discomforts include muscle soreness, pain, fatigue, or emotional discomfort. We will ask participants to complete an Exercise Participation Screener to determine exercise readiness. The certified yoga instructors are trained to provide guidance on modifications to make sure everyone can participate safely. In the rare event of an injury, research personnel will assist the participant to make an appointment at the UNM LoboCare Clinic.

18.3. If applicable, indicate which procedures may have risks to an embryo or fetus should the subject be or become pregnant. If pregnancy testing or birth control provisions are required, describe these.

N/A

18.4. If applicable, describe risks to others who are not subjects.

N/A

18.5. Describe the steps being taken to minimize the probability or magnitude of risks.

Note: All risks described here should also be described in the consent document.

19. Potential Benefits to Subjects

19.1. Describe the potential benefits that individual subjects may experience from taking part in the research. Include as may be useful for the IRB's consideration, the probability, magnitude, and duration of the potential

benefits. Note: Compensation for research participation is not considered a benefit.

19.2. Indicate if there is no direct benefit. Do not include benefits to society or others in this section.

Note: All potential benefits described here should also be described in the consent document.

Participants will be participating in either meditation or yoga which may provide them with direct individual benefits. It has long been established that mindfulness practices like meditation and yoga are associated with positive mental health outcomes.^{8,9} Mindfulness practices are also associated with improved physiologic function including autonomic nervous system (ANS) function.¹³

20. Recruitment Methods

20.1. Describe when, where, and how potential subjects will be recruited.

20.2. Describe the methods that will be used to identify potential subjects (e.g., chart review, referral, etc.).

20.3. Describe materials that will be used to recruit subjects (e.g., emails, scripts, advertisements, brochures, flyers, etc.). Attach draft copies of the documents or audio or video recordings with the application. Once the draft has been approved, the final copy of the printed material, audio or video recording must be submitted for review and approval prior to implementation. Please see Worksheet HRP-315 for information on advertisement standards. The preference is recruitment materials are submitted on Word document(s), however, this is not required when not possible. Clarify accordingly in this section.

We will recruit participants from the UNM HSC. The UNM CON currently employs 71 faculty and 71 staff with additional nurse faculty and staff within the HSC.

Participants will be recruited in-person during monthly faculty, staff, and all college meetings. We will also recruit participants through college email listservs using IRB approved flyers (see Attachment D) and by posting IRB approved fliers in common areas of the CON and Public Health Excellence Building. Interested participants will be contacted by study staff and screened for eligibility.

21. Provisions to Protect the Privacy Interests of Subjects

21.1. Describe the steps that will be taken to protect subjects' privacy interests.

"Privacy" refers to persons and their interest in controlling the access that others have to themselves. For example, based on their privacy interests, people may want to control:

- *The time and place/setting where they are examined or provide information*
- *The nature of the information they provide*
- *The nature of the experiences they are exposed to*

- *Who may observe or have access to information about them*

For example, individuals may not want to be approached for participation, provide responses to a research interview, or undergo a research procedure in a location where they may be seen or overheard.

The risk of loss of privacy is the greatest risk in this study. All reasonable attempts to maintain the privacy of participants will be taken.

Screening for study eligibility will take place in a private room with a closed door. This will occur in the Clinical Research Rooms housed within the CON Research Laboratory suite.

21.2. Describe the steps that will be taken to protect subjects' privacy including privacy protections during recruitment, consent, and data collection. Issues related to data are addressed in the Data Management/Confidentiality Section.

The consent process and the study visit will take place in a private room with a closed door in the Clinical Research Rooms housed within the CON Research Laboratory.

Only study members who have completed training will be authorized to administer informed consent and interviews.

22. Economic Burden to Subjects

22.1. *Describe any costs that subjects may be responsible for because of participation in the research. Clearly stipulate what procedures are standard of care and what procedures are research-related in the table below. Please place an X in the box for the responsible party for each procedure involved.*

List any costs to participants (or their 3rd party payer); include any charges for study procedures, visits, or drug/devices.

There is no cost to participants to participate in this study.

	Samples/Procedures	Study	3 rd Party Payer or Participant
_____	_____		
_____	_____		
_____	_____		
_____	_____		
_____	_____		
_____	_____		
_____	_____		
_____	_____		

22.2. List any other costs to participants not already described above.

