It is long been established that mindfulness practices like meditation and yoga are associated with positive mental health outcomes.^{8,9} In addition, mindfulness practices are known to support interpersonal relationships.¹⁰ In the workplace, mindfulness practice improves communication, builds a sense of shared goals leading to greater productivity and retention, and helps to decrease burnout.^{11,12} Furthermore, mindfulness practices foster resilience. Mindfulness practices are also associated with improved physiologic function including autonomic nervous system (ANS) function.¹³ Peripheral ANS activity, including cardiac vagal activity (indexed by heart rate variability [HRV]), regulates dynamic fine-tuning of feedback loops between emotion-related brain circuitry and the heart.¹⁴ HRV is known to be a robust biomarker of health, wellness, stress, and the ability to self-regulate.¹⁵ By instructing individuals in MBIs homeostasis in brain-heart feedback loops is promoted leading to autonomic stability.¹⁶ Given the potential impact of MBI to promote individual and workplace wellness, investigation of this intervention to improve wellness in academic faculty and staff is critical.

3. Study Design

3.1. Describe the study design (e.g., observational; randomized placebo-controlled clinical trial, etc.)

This study is a minimal-risk, single site, quasi-experimental study.

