The UNM CON currently employs 71 faculty and 71 staff and the HSC has additional nurse faculty and staff. We will employ a quasi-experimental design to assess feasibility, acceptability, and preliminary efficacy of MBIs (meditation; yoga) to increase a sense of belonging and connectedness in academic nursing faculty and staff. Using convenience sampling we will recruit and enroll 60 participants in to two study groups: 1) mindfulness mediation and 2) yoga. Interested study participants will be contacted by study staff and screened to determine study eligibility (See Attachment A). The screener is approximately 1-page in length and takes approximately 5 minutes to complete. The screener includes queries related to inclusion and exclusion criteria. Participants will also complete an Exercise Participation Screening (see Attachment B).¹⁷

Pre-data collection:

We will assign 15 individuals to each condition. Across both conditions, all participants will participate in one baseline assessment/training session, 6 weeks of MBIs (participants will be required to attend 2 sessions per week), and a post-intervention assessment session. Following screening for inclusion/exclusion criteria, eligible participants will complete the BEING Mindful Exercise participation screening. Eligible participants will provide informed consent.

After informed consent is obtained, research staff will allocate individuals to meditation vs yoga on 1:1 basis. If an individual is unable to participate in the yoga arm based on the BEING Mindful Exercise participation screening, they will be assigned to meditation and the next two participants will be assigned to yoga.

All participants will be given an anonymous study ID number once they are enrolled in the study. The only link between the study ID number and any identifier will be stored in a secure N:\Research-Studies network drive, in a folder to which only the investigators will have access. Any link between the study ID and identifiers will be destroyed when data analysis is complete.

Once we have enrolled 30 participants we will waitlist individuals for a second six-week intervention session after the completion of the first session. This will result in a possible enrollment 60 individuals.

12.3. For studies that collect existing or prospective data, describe the source of information, whether collected prospective or retrospectively.

Data collection:

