Description of Intervention Delivery

These guidelines detail the procedures used to conduct Mindful Meditation or Yoga sessions.

We will employ a quasi-experimental design to assess feasibility, acceptability, and preliminary efficacy of MBIs (meditation; yoga) to increase a sense of belonging and connectedness in academic nursing faculty and staff. We will assign 15 individuals to each condition. Across both conditions, all participants will participate in one baseline assessment/training session, 6 weeks of MBIs (participants will be required to attend 2 sessions per week), and a post-intervention assessment session. Following screening for inclusion/exclusion criteria, eligible participants will complete the **BEING Mindful** Exercise participation screening. Eligible participants will provide informed consent.

Assignment of Participants:

After informed consent is obtained, research staff will allocate individuals to meditation vs yoga on a 1:1 basis. If an individual is unable to participate in the yoga arm, they will be assigned to meditation and the next two participants will be assigned to yoga.

Retention:

To promote retention, we will reach out to participants with frequent reminders via text messages and emails.

Baseline Assessment session: During the baseline assessment session, participant characteristics will be collected. Baseline self-report questionnaires will be completed: 1) Sense of Belonging Scale (SBS); 2) Mindfulness Attention Awareness Scale (MASS) 15-item; 3) Generalized Anxiety Disorder-7 (GAD-7); 4) NIH toolbox measure of perceived stress.

Intervention Delivery:

The meditation and yoga interventions are 6-week protocols. We will offer meditation sessions 4 times per week and yoga sessions 4 times per week. We will require participants to attend two sessions per week. Attendance will be tracked via the Ilumivu platform. Participants will be requested to log attendance at each session via the app.

The meditation intervention will be led by [name] and [name]. Meditation is a practice of mental exercises designed to increase focus and cultivate a desire to relieve suffering in self and other.^{35,36} The practice dates back millennia to Buddhist and Hindu sages, but more recent work focuses on stress.³⁷ More recently, the term mindfulness has been used which means awareness, attention, and remembering.³⁷ Many religious traditions have a form of meditation based practice. This study will focus

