Aim 1: To assess precision of estimates, 95% confidence intervals will be calculated for rates of recruitment into study, retention to end of study, and participants completing all training sessions. Overall adherence will also be described by calculating the mean and standard deviation of the number of completed training sessions per participant. Qualitative Analyses: Qualitative descriptive analysis⁴⁰ will be used to create a comprehensive summary of the acceptability of the MBI to participants. Deductive analysis will be used to determine common themes related to acceptability in the domains of affective attitude, burden, ethicality, intervention coherence, opportunity costs, perceived effectiveness, and self-efficacy.⁴¹ Interview responses will be reviewed by two members of the research team to identify themes. Themes and preliminary interpretations will be regularly presented to the larger research team to resolve any discrepancies or disagreements and check for alternative interpretations.

Aim 2: Participant characteristics and baseline survey responses will be described using means and standard deviations (SD) for continuous variables and number (percentage) for categorical variables. Continuous intervention outcomes will be described using means and standard deviations and, due to sample size, difference scores from baseline for intervention outcomes will be compared between groups using non-parametric statistical tests. Cohen's d, as a descriptive statistic, will be used as an effect size measure to quantify the extent of within group and between group differences in means over time.⁴² Long-term HRV (time domain and frequency domain measures derived for each 5 minute epoch within a 24 hour period will be averaged) measures will be compared between meditation and yoga groups by t-test. EMA and HRV data will be merged into a single dataset, matching upon timestamp.

Five-minute heart rate epochs immediately following completion of each mEMA survey will be selected for analysis.^{20,34}

13.2. Provide a power analysis, if applicable.

14. Provisions to Monitor the Data to Ensure the Safety of Subjects

This section is required when research involves more than Minimal Risk to subjects. Describe:

N/A – The PI believes this study constitutes no more than minimal risk for potential participants. Therefore, a Data and Safety Monitoring Plan is not required.

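### Staff allocate to meditation or yoga with no described random or concealed sequence, and a make-up rule reveals the next two places, so the arm comparison is open to selection bias of unknown size

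*Combined protocol and SAP*

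**What the plan says.** Section 12.2 (Pre-data collection) states that after consent "research staff will allocate individuals to meditation vs yoga on 1:1 basis". Section 12.5 (Assignment of Participants) repeats it: "research staff will allocate individuals to meditation vs yoga on a 1:1 basis". Neither section says how the order is produced, who holds it, or whether it is hidden from the people enrolling. Section 3.1 describes the design: "This study is a minimal-risk, single site, quasi-experimental study". The blinding heading, 3.2, has no entry.

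Both sections add a make-up rule. When someone cannot take part in yoga, "they will be assigned to meditation and the next two participants will be assigned to yoga". The target is stated as "We will assign 15 individuals to each condition" in each of two cohorts of 30, and of the second cohort the plan says "This will result in a possible enrollment 60 individuals".

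For Aim 2, section 13.1 says that "difference scores from baseline for intervention outcomes will be compared between groups using non-parametric statistical tests", and that long-term HRV "measures will be compared between meditation and yoga groups by t-test". Cohen's d is descriptive. No covariate adjustment is planned, although section 12.3 collects prior mindfulness practice, physical ability and faculty or staff role at baseline.

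**The concern.** A between-arm test supports a statement about the practices only if the arms differ by chance apart from the practice. Here nothing described prevents the order of enrolment or the choice of arm from depending on the person. The exercise screen is completed before consent and allocation, so its result is available when the arm is assigned. Section 12.3 lets the principal investigator or trained personnel hold the consent meeting, and section 9.1 says the principal investigator leads yoga, so enrolment is not separated from delivery of an arm. Strict alternation, the kindest reading, is still predictable: someone who knows the next place can decide whom to consent next. After each use of the make-up rule, two consecutive places are known.

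The rule has a second effect. People who cannot do yoga are found only in meditation. If they respond differently, the arms differ for that reason alone.

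At stake are the Aim 2 tests and the between-group d. Section 13.1 says the pilot is to supply estimates for a later power analysis, so a distorted d could be carried forward.

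**Working it through.** **No figure to reproduce.** The plan gives no estimate of allocation bias and no power calculation. Section 5.3 rests the 30 participants on pilot-study advice for a medium between-group effect. The sizes below rest on assumptions, shown as ranges.

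**Set-up.** Simulation of 4,000 trials per setting, outcome SD 1, no true difference between arms, Mann-Whitney test at two-sided 0.05 (standing in for the unnamed non-parametric test). Bias is mean yoga minus mean meditation, in SD.

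**Route A: allocation related to prognosis.** Assumed: the log-odds of being placed in yoga rise by 0, 0.5 or 1.0 per SD of a prognostic score, and that score correlates 0.3 or 0.5 with the change score. The make-up rule is not used here.

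| Log-odds per SD | Correlation | N=30: bias, type I error | N=60: bias, type I error |
|---|---|---|---|
| 0 | 0.3 | 0.002, 4.3% | 0.006, 4.8% |
| 0 | 0.5 | -0.004, 4.4% | 0.000, 4.2% |
| 0.5 | 0.3 | 0.113, 5.9% | 0.135, 7.6% |
| 0.5 | 0.5 | 0.198, 7.6% | 0.219, 12.6% |
| 1.0 | 0.3 | 0.205, 7.2% | 0.215, 11.8% |
| 1.0 | 0.5 | 0.352, 14.4% | 0.368, 28.3% |

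Without steering the bias is zero within simulation error. With it, the bias is about 0.1 to 0.4 SD.

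**Route B: the make-up rule alone.** Let f be the fraction of enrolled people who cannot do yoga and δ the amount by which their mean change is worse. All of them sit in meditation, about half the sample, so their share of that arm is about 2f and

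bias ≈ 2f × δ.

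With f = 0.10 or 0.20 and δ = 0.5 or 1.0 (assumed): 0.20 × 0.5 = 0.10; 0.20 × 1.0 = 0.20; 0.40 × 0.5 = 0.20; 0.40 × 1.0 = 0.40 SD. Simulation at N=30 agrees:

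| f, δ | Alternation with rule | Randomised, rule kept | Randomised, only those able to do yoga compared |
|---|---|---|---|
| 0.10, 0.5 | 0.101, 5.1% | 0.115, 5.9% | -0.003, 4.4% |
| 0.10, 1.0 | 0.209, 7.6% | 0.216, 8.1% | -0.012, 4.8% |
| 0.20, 0.5 | 0.203, 7.4% | 0.214, 7.7% | 0.001, 4.1% |
| 0.20, 1.0 | 0.399, 16.1% | 0.435, 18.5% | 0.002, 5.0% |

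At N=60 the biases are nearly the same, but type I error reaches 29.5% (alternation with rule) and 32% (randomised, rule kept), against 4.0% to 5.7% in the last scheme. Randomising and keeping the rule therefore leaves this bias in full. If δ = 0 or nobody is unable to do yoga, Route B contributes nothing.

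**Scale.** The standard error of a difference in means is √(2/15) = 0.37 SD at 15 per arm and √(2/30) = 0.26 SD at 30 per arm. A bias of 0.4 SD is about one standard error in one cohort and about one and a half in both combined.

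**The rule and the 1:1 target.** Suppose places alternate. If the person who cannot do yoga arrives when yoga is due, meditation replaces it and two yoga places follow; the counts level out. If meditation was due anyway, two yoga places still follow and yoga finishes one ahead.

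**The case against.** The strongest reply has four parts.

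- **The text does not say staff choose.** A reader might infer that staff pick the arm by judgement, or that nobody is asked for a preference. The plan states neither. A 1:1 count with a compensating rule fits mechanical alternation at least as well, and Route A gives zero bias without steering. This stands: the supportable claim is that no random or concealed mechanism is described.
- **The design is declared.** A reader might infer a contradiction or a false claim of randomisation. There is none. This stands, but the label does not protect the planned tests.
- **The arm contrast is not what the study is for.** The primary outcomes in section 7.1 are feasibility and acceptability, and the Aim 2 hypotheses in section 1.1 are pre-post. This largely stands and limits the weight of the point. The arm contrast is nevertheless the only thing section 13.1 tests for Aim 2.
- **Small randomised arms are unbalanced too.** For a trait with assumed 50% prevalence and 15 per arm, a gap of 20 points means at least 3 people. The count difference has SD √(30 × 0.25) = 2.74, so the chance is about 2 × [1 − Φ(2.5/2.74)] = 36%. At 30 per arm (at least 6 people, SD √(60 × 0.25) = 3.87) it is 2 × [1 − Φ(5.5/3.87)] = 16%. This is correct, but such imbalance has no systematic direction and the test's error rate allows for it. Steering has a direction and is not allowed for.

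**Conclusion.** The point holds as a design weakness that is cheap to improve before enrolment and cannot be repaired afterwards by changing the allocation. The yoga-versus-meditation comparisons are open to selection bias whose size the documents cannot settle. It is zero if allocation is unrelated to prognosis and people who cannot do yoga change like the rest; it is roughly 0.1 to 0.4 SD under the assumed steering, or under the make-up rule with 10% to 20% unable to do yoga and a deficit of 0.5 to 1.0 SD.

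It is tempting to go further and say that randomisation by itself would remove the problem. The documents do not support that: the make-up rule would override a random list for two places each time and would leave one kind of participant in meditation only. Nor does the point undermine the Aim 1 feasibility results, which are largely unaffected. Randomising between two active arms also does not help the pre-post hypotheses, which have no untreated control, or address unblinded self-report or dropout.

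**What to change.** In sections 12.2 and 12.5, replace the allocation sentence and delete the rule about the next two participants. Suggested wording: after consent, participants cleared for both practices are randomised 1:1 from a computer-generated list in permuted blocks within each cohort, prepared by someone outside recruitment, held in REDCap and revealed one assignment at a time. Stratifying by faculty or staff is optional.

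In section 13.1, add that participants who cannot do yoga may be enrolled in meditation and counted for feasibility and within-group description, but are left out of the between-arm tests and the between-group Cohen's d. Update section 3.1 to match, and state 15 per arm as a target.

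The cost is a short set-up and someone outside recruitment to prepare the list; the documents do not say who that could be. No added participants or visits are needed. Group sizes will move away from 15:15: with 3 of 30 unable to do yoga, 27 are randomised and meditation holds 16 or 17 against 14 or 13 in yoga; with 6 of 30, it is 18 against 12. The comparison then uses 24 to 27 of 30 people, which widens its standard error by a factor of √(30/27) = 1.05 to √(30/24) = 1.12.
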